3.6 Discontinuation from Study

Subjects should be discontinued from the study for 1 of the following primary reasons:

- Withdrawal of consent
- Lost to Follow-up
- Death
- Subject noncompliance with protocol
- Administrative study closure
- Completed study

Confidential Page 32 of 78

3.7 Treatment Beyond Disease Progression

Subjects will be permitted, with the Sponsor's approval, to continue with treatment beyond initial RECIST 1.1 defined PD as long as they meet the following criteria:

- Investigator-assessed clinical benefit from the treatment;
- Subject is clinically stable;
- Subject is tolerating study drug; and
- There is agreement with the sponsor.

The assessment of clinical benefit should take into account whether the subject is clinically deteriorating and unlikely to receive further benefit from continued treatment. The following criteria need to be taken into consideration:

- Absence of clinical symptoms and signs (including worsening of laboratory values) indicating disease progression.
- No decline in ECOG performance status.
- Absence of rapid progression of disease or of progressive tumor at critical anatomical sites (e.g., cord compression) requiring urgent alternative medical intervention.

Subjects should discontinue study therapy upon evidence of further progression, defined as an additional 10% or greater increase in tumor burden from time of initial progression (including all target lesions and new measurable lesions).

Imaging is required every 6 weeks (± 3 days) for those subjects with confirmed PD who remain on AGEN1884 until treatment is discontinued.

4. Investigational Agent

4.1 Description of Investigational Agent

AGEN1884 is a novel, fully human monoclonal IgG1 antibody designed to block CTLA-4. It will be supplied as 50 mg per vial. AGEN1884 should be stored in a refrigerator at 2°C to 8°C.

4.1.1 Dosage and Administration

AGEN1884 will be administered intravenously (IV) for each cycle (3 weeks) as a 60-min (-10/+20 min) infusion. Infusions will be followed immediately by a 15-min saline flush of the IV line.

Treatment will be administered every 3 weeks for the first 4 cycles.

At the 12-week evaluation timepoint, subjects may continue to receive AGEN1884 every 3, 6, or 12 weeks (\pm 7 days) for a maximum duration of 1 year of treatment, provided they were not diagnosed with PD and were tolerating the study drug. The appropriate schedule will be based on discussion with the medical monitor. Subjects who progressed yet still have clinical benefit from treatment may continue on treatment following discussion with, and approval of, the medical monitor. For detailed criteria and consideration for treatment post-progression, refer to Section 3.7. Dosing is described in Table 1.

Please refer to the Pharmacy Manual for further instructions on AGEN1884 dosage and administration.

Confidential Page 33 of 78

4.1.2 Dosing Delay Criteria

Prior to every AGEN1884 administration, laboratory values will be reviewed. AGEN1884 administration will be delayed for the following adverse events (AEs), if the following AEs occur on the day of planned AGEN1884 dosing:

- Either febrile neutropenia or neutropenia <500 cells/mm³ for >1 week despite the use of growth factors.
- Any grade ≥2, non-skin, drug-related AE except for fatigue and laboratory abnormalities
- Any grade 3 drug-related laboratory abnormality (except lymphopenia, AST, ALT, total bilirubin, or asymptomatic lipase or amylase).
 - o Grade 3 lymphopenia does not require a dose delay.
 - o If the subject has a baseline AST, ALT, or total bilirubin that is within normal limits, dosing should be delayed for drug-related grade ≥2 toxicity.
 - o If the subject has a baseline AST, ALT, or total bilirubin within the grade 1 toxicity range, dosing should be delayed for drug-related grade ≥3 toxicity.
 - o Any grade 3 drug-related amylase or lipase abnormality that is not associated with symptoms or clinical manifestations of pancreatitis does not require dose delay.
- Any grade 3, skin, drug-related AE.
- Any AE, laboratory abnormality, or intercurrent illness that, in the judgment of the investigator, warrants delaying the dose of study medication.
- For subjects in Phase 2 with HCC and an elevated baseline liver function test:

Dose delay for the following:

- Baseline AST, ALT \leq 2 x ULN with an increase to \geq 5 x ULN
- Baseline AST, ALT ≥ 2 x ULN with an increase to ≥ 3 x the baseline level
- Elevations of AST, ALT ≥500 IU/L or 20 x ULN regardless of baseline level
- Baseline total bilirubin ≤ 1.5 x ULN and increase to ≥ 2 x ULN
- Baseline total bilirubin >1.5 x ULN and increase to \geq 2 x baseline level
- Elevations of total bilirubin $\ge 3x$ ULN regardless of baseline level

Permanently discontinue for

- Elevations of ALT ≥20 x ULN regardless of baseline level
- Clinical Hepatic Decompensation regardless of lab values as follows:
 - New onset clinical ascites
 - Upper gastrointestinal bleeding due to portal hypertension
 - o Encephalopathy
 - Coagulopathy due to liver disease
 - Worsening Child-Pugh score to 9

Confidential Page 34 of 78

Subjects in Phase 2 with HCC will be followed closely and the appropriate course of action (including but not limited to hospitalization and/or consultation with a hepatologist) will be implemented as clinically indicated. In addition, other common causes of hepatic dysfunction should be ruled out; if a diagnoses of autoimmune hepatitis (AIH) is made, see Table 6 for additional management guidelines.

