4.3.4 Hepatic irAEs

Rule out non-inflammatory causes (e.g., alcohol use, acute viral hepatitis, flare up from chronic hepatitis, co-infection [e.g., with hepatitis D], etc.). If a non-inflammatory cause is identified, treat accordingly and continue therapy per protocol. Consider imaging for obstruction and a hepatologist consult (Table 6).

Table 6: Hepatic ir AE Management Algorithm

	Hepatic irAEs										
CTCAE Grade of Liver Test Elevation	Management	Follow-Up									
Grade 1 AST or ALT >ULN to 3 x ULN and/or total bilirubin >ULN to 1.5 x ULN.	Continue AGEN1884 therapy per protocol.	 Continue liver function tests (LFT) monitoring per protocol. If worsens: Treat as grade 2 or grade 3-4. 									
Grade 2 AST or ALT >3 to ≤5 x ULN and/or total bilirubin >1.5 to ≤3 x ULN. If subject has concurrent AST or ALT >3 x ULN and total bilirubin >2 x ULN, discontinue AGEN1884 therapy per protocol (Hy's Law)	 Delay AGEN1884 therapy per protocol. Increase frequency of monitoring to every 3 days. 	If returns to baseline: Resume routine monitoring; resume AGEN1884 therapy per protocol. If elevations persist >5 to 7 days or worsen: 0.5-1 mg/kg/day methylprednisolone IV or oral equivalent. When LFT returns to grade 1 or baseline, taper corticosteroids over ≥1 month, consider prophylactic antibiotics for opportunistic infections, and resume AGEN1884 therapy per protocol.									
Grade 3-4 AST or ALT >5 x ULN and/or total bilirubin >3 x ULN.	 Permanently discontinue AGEN1884 therapy per protocol. Increase frequency of monitoring to every 1-2 days. 1-2 mg/kg/day methylprednisolone IV or oral equivalent.* Add prophylactic antibiotics for opportunistic infections. Consult gastroenterology. Consider obtaining MRI/CT scan of liver and liver biopsy if clinically warranted. 	 If returns to grade 2: Taper corticosteroids around 4 to 6 weeks. If does not improve in >3 to 5 days, worsens, or rebounds: Add mycophenolate mofetil 1 g twice daily. If no response within an additional 3-5 days, consider other immunosuppressants per local guidelines. 									

Confidential Page 41 of 78

	Hepatic irAEs	
CTCAE Grade of Liver Test Elevation	Management	Follow-Up

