For subjects in Phase 2 with HCC and elevated baseline LFT Dose delay for the following: Baseline AST, ALT < 2 x ULN with an increase to ≥ 5 x ULN Baseline AST, ALT ≥ 2 x ULN with an increase to >3 x the baseline level Elevations of AST, ALT ≥ 500 IU/L or 20 x ULN regardless of baseline level Baseline total bilirubin ≤ 1.5 x ULN and increase to ≥ 2 x ULN Baseline total bilirubin >1.5 x ULN and increase to ≥ 2 x baseline level Elevations of total bilirubin ≥ 3 x ULN regardless of baseline level	Dose delay or discontinue AGEN1884 therapy. 1-2 mg/kg/day methylprednisolone IV or oral equivalent.* Consider hepatologist consult Increase frequency of monitoring to every 3 days	 If returns to grade <1 or baseline level within 1 week then taper corticosteroids over ≥ 1 month If symptoms and laboratory resolve to grade ≤1 or baseline levels and steroids have been tapered to a prednisone level ≤ 10mg/day or equivalent for at least a week, may consider resuming AGEN1884 If does not improve in >3 to 5 days, worsens, or rebounds: Add mycophenolate mofetil 1 g twice daily. If no response within an additional 3-5 days, consider other immunosuppressants per local guidelines and hepatologist consult. Also, permanently discontinue. If symptoms and laboratory do not resolve to grade ≤1 or baseline levels within 3 weeks or steroids cannot be tapered to a prednisone level ≤ 10 mg/day or equivalent within 9 weeks, AGEN1884 must be permanently discontinued. All cases considered for re-treatment should be discussed with the medical monitor

^{*} The recommended starting dose for grade 4 hepatitis is 2 mg/kg/day methylprednisolone IV.

ALT: alanine aminotransferase; AST: aspartate aminotransferase; CT: computed tomography; CTCAE: Common Terminology Criteria for Adverse Events; HCC: hepatocellular carcinoma; irAE: immune-related adverse event; IV: intravenous; kg: kilogram; LFT: liver function test; mg: milligram; MRI: magnetic resonance imaging; ULN: upper limit of institutional normal.

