4.4.2 Permanent Treatment Discontinuation

The following ADRs require permanent treatment discontinuation of AGEN1884:

Any grade 4 ADRs except for single laboratory values out of normal range that are unlikely related to trial treatment as assessed by the investigator, do not have any clinical correlate, and resolve within 7 days with adequate medical management.

Any grade 3 ADRs except for any of the following:

- Transient (≤6 hours) grade 3 flu-like symptoms or fever, which are controlled with medical management.
- Transient (≤24 hours) grade 3 fatigue, local reactions, headache, nausea, or emesis that resolves to grade ≤1.
- Single laboratory values out of normal range (excluding grade ≤3 liver function test increase) that are unlikely related to trial treatment according to the investigator; do not have any clinical correlate; and resolve to grade ≤1 within 7 days with adequate medical management.
- Tumor flare phenomenon, defined as local pain, irritation, or rash localized at sites of known or suspected tumor.
- Any grade ≥3 drug-related amylase or lipase abnormality that is not associated with symptoms, or clinical manifestations of pancreatitis does not require dose delay. The trial medical monitor should be consulted for such grade ≥3 amylase or lipase abnormalities.
- Increases in ECOG performance status to ≥3 that do not resolve to ≤2 by Day 14 of the following cycle (infusions should not be given on the following cycle if ECOG performance status is ≥3 on day of study drug administration).

Any grade 2 ADR should be managed as follows:

- If a grade 2 ADR resolves to grade ≤1 by the last day of the current cycle, trial treatment may continue.
- If a grade 2 ADR does not resolve to grade ≤1 by the last day of the current cycle, infusions should not be administered during the following cycle. If, at the end of the following cycle, the event has not resolved to grade 1, the subject should permanently discontinue treatment with AGEN1884.
- For grade 2 ADRs related to hormone insufficiencies that can be managed by replacement therapy, up to 2 subsequent doses may be omitted.
- Upon the second occurrence of the same grade 2 ADR (except for hormone insufficiencies that can be managed by replacement therapy) in the same subject, treatment with AGEN1884 should be permanently discontinued.

Confidential Page 46 of 78

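### For Phase 2 HCC subjects with an elevated baseline liver test, the protocol is inconsistent on whether AST ≥20 x ULN permanently ends treatment

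*Protocol*

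**What the plan says.** Three places in the protocol govern the same laboratory result.

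- **Section 4.1.2 (Dosing Delay Criteria)** has an HCC block that opens "For subjects in Phase 2 with HCC and an elevated baseline liver function test". Its delay list includes "Elevations of AST, ALT ≥500 IU/L or 20 x ULN regardless of baseline level". Its permanent-stop list, directly below, has one laboratory item, "Elevations of ALT ≥20 x ULN regardless of baseline level", followed by five signs of hepatic decompensation.
- **Section 4.3.4, Table 6, HCC row** repeats the delay triggers for the same subjects. The action is "Dose delay or discontinue AGEN1884 therapy". If values recover to grade ≤1 or baseline and steroids are down to prednisone ≤10 mg/day or equivalent for at least a week, the site "may consider resuming AGEN1884". The row adds: "All cases considered for re-treatment should be discussed with the medical monitor".
- **Section 4.4.2 (Permanent Treatment Discontinuation)** has a list for all Phase 2 HCC subjects, whatever their baseline. It states in mandatory terms that they are to be discontinued for ALT or AST ≥20 x ULN, and for the same five signs of decompensation.

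Subjects with elevated baselines are expected: inclusion criterion 9 admits HCC subjects with AST and ALT up to 5 x ULN.

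**The concern.** Whether a subject with liver cancer may be re-exposed to a CTLA-4 antibody after a very large transaminase rise should have one answer. Here the answer depends on which section the site opens. A site that works from Section 4.1.2 and Table 6 could resume the drug after recovery from AST ≥20 x ULN. A site that works from Section 4.4.2 could not. Each could point to protocol text in support.

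Safety and tolerability are the Phase 2 primary objective. The medical monitor, who is to be consulted before re-treatment, is not told which rule to apply. The deviation review in SAP Section 8.4 likewise has no clear standard for a subject who resumed.

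**Working it through.** No arithmetic applies and the plan states no figure to reproduce. The check is a comparison of the rules for a Phase 2 HCC subject with an elevated baseline test.

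| Result | Section 4.1.2 | Table 6, HCC row | Section 4.4.2, HCC list |
|---|---|---|---|
| AST ≥20 x ULN | Delay only; the stop list omits AST | Delay or discontinue; conditional resumption | Permanent stop |
| ALT ≥20 x ULN | Listed under both delay and permanent stop | Delay or discontinue; conditional resumption | Permanent stop |

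1. **Is AST really missing from the Section 4.1.2 stop list?** Yes. The delay line names both enzymes and the stop line names only ALT. The five decompensation items match those in Section 4.4.2, so AST is the only difference in content between the two stop lists. That looks like a drafting slip.

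2. **Does the HCC row contain the stop implicitly?** No. It has its own permanent stops: no response to added immunosuppression, values not resolved to grade ≤1 or baseline within 3 weeks, and steroids that cannot be tapered to the prednisone limit within 9 weeks. A peak of 20 x ULN is not among them, although 20 x ULN is one of the row's delay triggers.

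3. **Do the cross-references lead to Section 4.4.2?** No. The laboratory footnote to the Schedule of Assessments (Table 10) sends sites to Section 4.1.2 before each dose. The text after the Section 4.1.2 list sends them to Table 6 if autoimmune hepatitis is diagnosed. Neither Section 4.1.2 nor the HCC row cites Section 4.4.2, and no order of precedence is stated.

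4. **Who is affected?** Only HCC subjects with an elevated baseline test, because the Section 4.1.2 block and the HCC row are confined to them. About 20 HCC subjects are planned. More may be enrolled to complete the PK subgroup, so 20 is not a ceiling. The documents give neither the share with an elevated baseline nor a rate of AST ≥20 x ULN. The number affected therefore cannot be estimated; it may be 0.

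**The case against.** The strongest reply is that all three rules can be obeyed together. Section 4.1.2 governs the dose due that day, so a site can delay that dose and then stop under Section 4.4.2. Permission to consider resuming does not override a mandatory stop, and Section 4.3 presents its algorithms as help for investigators. On this reading what remains is one missing word and one missing cross-reference.

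Much of this stands. Section 4.4.2 probably prevails, and for ALT the overlap of the delay and stop lists inside Section 4.1.2 is not an error. But the reader has to infer precedence, and Section 4.1.2 goes beyond delay: it carries its own permanent-stop list, which leaves AST out.

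The safeguards also stand. Every rule withholds the immediate dose. Resumption under Table 6 needs recovery, a steroid taper and discussion with the medical monitor, and the 3-week and 9-week limits force a stop otherwise.

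A further reply is that a general rule already covers the case. Section 4.4.2 stops "Any grade 3 ADRs except for any of the following", and the general part of Table 6 places "AST or ALT >5 x ULN and/or total bilirubin >3 x ULN" at grade 3-4, with permanent discontinuation. This is a partial backstop at most. The Section 4.4.2 rule reaches only drug-related rises, and it is not stated that the general-row grading applies to subjects who have their own row because their baseline is raised.

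From the same two passages a reader might infer a second conflict, for drug-related values above 5 and below 20 x ULN, where the HCC row allows resumption and the general grade 3 stop has no HCC exception. The documents do not support that. The HCC row assigns no grades to its triggers, the CTCAE version 5 liver criteria are not reproduced, and it is ordinary to read a specific HCC row as modifying a general rule. Nor can the limits of such a band be fixed from multiples of baseline alone, because the 500 IU/L trigger also applies and no ULN in IU/L is given.

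**Conclusion.** The inconsistency is real on the current text and is minor. For AST ≥20 x ULN, Section 4.1.2 lists a delay, the Table 6 HCC row leaves resumption open, and Section 4.4.2 requires a permanent stop. For ALT ≥20 x ULN, only Table 6 is out of line.

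A reader might go further and infer that the protocol authorises re-treatment against Section 4.4.2, or dosing while enzymes are at that level. It does neither: the wording of Section 4.4.2 is mandatory, that of Table 6 is permissive, and no rule allows the immediate dose.

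The conclusion rests on the wording alone and needs no assumption about event rates. It concerns one cohort of about 20 subjects, with an unknown and possibly zero number affected. Sample size, analysis sets and statistical methods are unchanged.

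**What to change.** Make two wording edits in one protocol amendment:

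1. In Section 4.1.2, change the laboratory item in the permanent-stop list to: *ALT or AST ≥20 x ULN regardless of baseline level.*
2. In the Table 6 HCC row, add: *ALT or AST ≥20 x ULN: permanently discontinue, no resumption (Section 4.4.2).*

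The cost is the amendment itself, with no change to the SAP. The downside is that a few subjects who recover from such a rise could not resume, which Section 4.4.2 already requires.

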4.2 Infusion Reactions

Subjects receiving AGEN1884 should be monitored for infusion reactions. This includes the measurement of vital signs for ≥1 hour after infusion, defined as 1 hour after the completion of the 60-minute infusion of AGEN1884 and the 15-minute flush that follows the infusion. Subjects will remain in the clinic under close supervision for the duration of this monitoring period. Subjects with mild or moderate infusion reactions may receive AGEN1884 with close monitoring. Premedication with an antipyretic or antihistamine may be considered. For severe infusion reactions, AGEN1884 infusion must be discontinued, and appropriate medical therapy should be administered.

Subjects who do not experience any grade ≥ 1 infusion-related toxicity during or after the infusion may be released from monitoring after 1 hour if they are otherwise stable. Subjects with any infusion-related toxicity must be managed as per the guidelines below, and monitoring will continue until any infusion-related toxicity has abated to grade <1 and ≥ 1 hour has passed from the completion of the entire infusion and flush. Before leaving the study site, all subjects will be given information on infusion-related toxicity per institutional guidelines. This will include instructions on when and how to return for immune-mediated toxicities associated with CTLA-4 blockade.

If mild or moderate infusion reaction occurs, the infusion should be interrupted, and supportive care should be administered until the symptoms resolve, per treating clinician.

Management guidelines for infusion reactions will be provided to the investigators at each site (Table 2).

Confidential Page 35 of 78

Table 2: Infusion Reaction Guidelines

CTCAE Grade	Treatment	Premedication at Subsequent Dose Administration
Grade 1 Mild reaction; infusion interruption not indicated; intervention not indicated.	Increase monitoring of vital signs as medically indicated until the subject is deemed medically stable in the opinion of the investigator.	None.
Grade 2 Requires infusion interruption but responds promptly to symptomatic treatment (e.g., antihistamines, nonsteroidal anti-inflammatory drugs [NSAIDs], narcotics, IV fluids); prophylactic medications indicated for ≤24 hours.	Stop infusion and monitor symptoms. Additional appropriate medical therapy may include but is not limited to the following: IV fluids Antihistamines NSAIDS Acetaminophen Narcotics Increase monitoring of vital signs as medically indicated until the subject is deemed medically stable in the opinion of the investigator. If symptoms resolve within 1 hour of stopping drug infusion, the infusion may be restarted at 50% of the original infusion rate. Otherwise, dose administration will be held until symptoms resolve, and the subject should be premedicated for the next scheduled dose. Subjects who develop grade 2 toxicity despite adequate premedication should be permanently discontinued from further study drug administration.	Subject may be premedicated 1.5 h (± 30 min) prior to infusion with the following: • Diphenhydramine 50 mg PO (or equivalent dose of antihistamine). • Acetaminophen 500-1000 mg PO (or equivalent dose of antipyretic).
Grade 3 Prolonged (i.e., not rapidly responsive to symptomatic medication and/or brief interruption of infusion); recurrence of symptoms following initial improvement; hospitalization indicated for other clinical sequelae (e.g., renal impairment, pulmonary infiltrates). Grade 4 Life-threatening; pressor or ventilatory support indicated.	Stop infusion. Additional appropriate medical therapy may include but is not limited to: IV fluids Antihistamines NSAIDs Acetaminophen Narcotics Oxygen Pressors Corticosteroid Epinephrine Increase monitoring of vital signs as medically indicated until the subject is deemed medically stable in the opinion of the investigator. Hospitalization may be indicated. Subject is permanently discontinued from further study drug administration.	No subsequent dosing.

CTCAE: Common Terminology Criteria for Adverse Events; h: hour; IV: intravenous; min: minute; NSAID: nonsteroidal anti-inflammatory drug, PO: orally.

Confidential Page 36 of 78

4.3 Management of Immune-Related Adverse Events

Immuno-oncology agents such as AGEN1884 are associated with immune-related adverse events (irAEs). Early recognition and management of irAEs may mitigate severe toxicity. Investigators should also monitor subjects closely for potential irAEs, which may manifest after weeks of treatment, at the earliest. Such events may consist of persistent rash, diarrhea, colitis, autoimmune hepatitis, pneumonitis, encephalitis, arthritis, glomerulonephritis, cardiomyopathy, or uveitis and other inflammatory eye conditions.

Management algorithms have been developed to assist investigators in assessing and managing the following groups of irAEs: gastrointestinal, pulmonary, dermatological, renal, hepatic, neurological, and endocrine, among others.

Adverse events (both non-serious and serious) associated with drug exposure and consistent with an immune phenomenon may represent an immunologic etiology. These irAEs may be predicted based on the nature of the study drugs, their mechanism of action, and reported experience with immunotherapies that have a similar mechanism of action. An irAE can occur shortly after the first dose or several months after the last dose of treatment. Particular attention should be paid to AEs that may be suggestive of potential irAEs, as outlined below.

